## 9.0 STATISTICAL METHODS

**Power Analysis.** Our power analysis is based on our primary aim to, “Examine the effect of 6 weeks of daily self-administered relaxing acupressure compared to self-administered sham acupressure or no treatment on persistent fatigue as measured with The Brief Fatigue Inventory.” Although we will run a larger model for the analysis, in the power calculation we focus on the specific components of the model in which we are interested. Towards that end, we compute the power via simulation using a mixed effects model with a between-subject factor group (3 levels), a within-subject factor week (0, 6, 12, and 24), group-by-time interaction and a random subject effect. The mean BFI at baseline is assumed to be 5.5, whereas values at end of treatment were assumed to be 4.5, 3.5, and 2, respectively for no treatment, sham acupressure and relaxing acupressure arms. The between-subject variance is assumed to be 4 at all time-points whereas the variance of the random subject component is taken to be 4 also (yielding an intra-class correlation of 0.5). These assumed values are estimates based on our pilot data. For this configuration, the power for detecting a significant week-by-group interaction is greater than 95% with a sample size of 50 evaluable participants per treatment arm (we anticipate a ~13 % drop out with the goal of 150 completers for a total sample size of 171) and a 5% level of significance. Such a model is able to detect a post-hoc difference between the relaxing acupressure and each of the other two arms with more than 90% power at a reduced 0.01 level of significance in order to protect against Type I error probability inflation. In the second phase after the treatment period, it is anticipated that both the no-treatment and the sham acupressure arms will experience a bounce

back close to the baseline level, while the relaxing acupressure arm will maintain its end-of-treatment average. Thus, the differences will be more pronounced than those in the active treatment phase, and we will be well

powered to detect the effect size.

We also want to power the study to allow us to observe differences in sleep parameters. The extent of overlap between fatigue and sleep disturbances in ovarian cancer survivors is currently unknown. Research indicates that anywhere from 55 to 67% of ovarian cancer survivors experience sleep disruptions. While fatigued women are most likely enriched with individuals experiencing sleep disturbances we will conservatively assume that roughly 50% of women will have some significant sleep disturbances per treatment arm. As such, with 50 women per treatment group we will be overpowered for detecting a difference in fatigue and sufficiently powered to detect changes in sleep measures. For example, using the PSQI as a basis for powering differences in sleep quality from previous studies the mean PSQI in female cancer survivors ranges from  $6.84 \pm 0.376$  to  $7.16 \pm 0.325$ . A 1-point decrease in the PSQI from ~7 to ~6 is considered a clinically significant difference. The mean PSQI values at baseline is assumed to be 7 in all arms whereas the means are taken to be 7, 6, and 5 at 6 weeks in the no treatment, sham and relaxing acupressure arms, respectively. Assuming an intra-subject correlation of 0.5, we have powers above 95% to detect differences between any pair of arms at 1% level of significance.

All power calculations are carried out on the basis of 100 simulations in the software PASS 2008 (NCSS, Kaysville, Utah 84037, USA).

**9.1 Definition of an Evaluable Participant.** Evaluable participants must complete both the baseline and week 6 BFI.

**9.2. Post-hoc Power Analysis.** Average changes in BFI between baseline and 6 weeks for both true and sham acupressure were statistically significant at 5% level, so power was not an issue in detecting these effect sizes. It is evident from Table 4 that although it did not reach statistical significance, the difference between true and sham acupressure was trending towards that ( $p = 0.08$ ). It turns out that with the mean of the changes estimated to be that obtained in the data (Table 3), in order to detect a difference between the two Acupressure arms with 80% power, we would have needed 94 subjects per arm. The calculation is based on a two-sample t-test with a pooled standard deviation estimate of 1.7.

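### Section 9.0 credits its BFI variances (4 and 4, ICC 0.5) to the pilot, but they imply a change SD of 2.83 against the pilot's printed 1.5 to 2.2, and at week 6 they do not give the stated power above 90% against sham

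*Combined protocol and SAP*

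**What the plan says.** Section 9.0 (Power Analysis) describes a mixed model with group, week (0, 6, 12, 24), their interaction and a random subject effect. On the means it says "The mean BFI at baseline is assumed to be 5.5", and "values at end of treatment were assumed to be 4.5, 3.5, and 2, respectively for no treatment, sham acupressure and relaxing acupressure arms".

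On variability it names a between-subject variance of 4 at every time point, "whereas the variance of the random subject component is taken to be 4 also (yielding an intra-class correlation of 0.5"). It gives the source as follows: "These assumed values are estimates based on our pilot data", with a citation to the pilot (reference 21).

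Two power claims follow for 50 evaluable women per arm. The first is that "the power for detecting a significant week-by-group interaction is greater than 95" per cent, "and a 5% level of significance". The second is that the model can "detect a post-hoc difference between the relaxing acupressure and each of the other two arms". The plan puts a figure and a stricter threshold on this second claim: "with more than 90% power at a reduced 0.01 level of significance". All power figures rest on 100 simulations.

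The pilot itself is summarised in section 1.0. BFI reductions were 4.0 (SD 1.5) with relaxing, 2.2 (SD 1.6) with high-intensity stimulating and 2.7 (SD 2.2) with low-intensity stimulating acupressure, in 14, 15 and 14 participants. The caption of Figure 2 shows that change runs from week 0 to week 12.

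**The concern.** A group-by-week comparison is driven by the variance of change within a woman, not by the spread at a single visit. The printed inputs fix that change variance, and it is far larger than the pilot's own change SDs allow. A reader who checks the plan from its printed variances cannot recover the second power claim for the comparison with sham, the arm that isolates the specific effect of the acupoints.

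At stake is how a non-significant relaxing-versus-sham result would be read. With the printed variances, 50 per arm looks too few for a 1.5-point difference; with the pilot's pooled SD it looks sufficient. The plan should not leave both readings open.

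**Working it through.** **Inputs.** From section 9.0: reductions by week 6 of 1.0, 2.0 and 3.5 (5.5 minus 4.5, 3.5 and 2), so 1.5 points for relaxing versus sham and 2.5 for relaxing versus no treatment; variances 4 and 4; ICC 0.5; 50 per arm; alpha 0.05 (interaction) and 0.01 (pairwise, taken as two-sided because sidedness is not stated). From section 1.0: the pilot SDs and arm sizes.

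**1. Change SD implied by the printed inputs.** ICC = subject / (subject + residual), so 0.5 = 4 / (4 + residual) and the residual variance is 4. With a random subject effect, change between two visits has variance 2 × 4 = 8, SD 2.83. The variance labelled between-subject is therefore acting as the residual variance.

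**2. Reproducing the interaction power.** The reductions average 2.167, and their squared deviations sum to 3.167. Noncentrality = 50 × 3.167 / 8 = 19.8 on (2, 147) df, which gives 98% at 0.05 for weeks 0 and 6. With all four weeks and the week-6 means maintained it is 99%. The stated figure above 95% is reproduced. With the pilot SD it exceeds 99.9%.

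**3. Change SD in the pilot.** (13 × 1.5² + 14 × 1.6² + 13 × 2.2²) / 40 = 128.01 / 40 = 3.20, so the pooled SD is 1.79 and the residual variance 3.20 / 2 = 1.6. The 95% interval for the change variance (chi-square, 40 df) is 2.16 to 5.24, which excludes 8. The printed residual variance is 4 / 1.6 = 2.5 times the pilot's.

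**4. Pairwise power at week 6.** Standard error = SD × √(2/50) = 0.2 × SD; noncentral t on 98 df, two-sided 0.01, difference 1.5.

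| Change SD | Source | SE | 1.5 / SE | Power |
|---|---|---|---|---|
| 1.5 | pilot, relaxing | 0.300 | 5.00 | 99% |
| 1.6 | pilot, high intensity | 0.320 | 4.69 | 98% |
| 1.79 | pilot, pooled | 0.358 | 4.19 | 94% |
| 2.2 | pilot, low intensity | 0.440 | 3.41 | 78% |
| 2.83 | printed 4 and 4 | 0.566 | 2.65 | 51% |

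For relaxing versus no treatment (2.5 points), SD 2.83 gives 96% and SD 1.79 more than 99.9%.

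**5. Can the printed inputs reach 90% against sham?** At week 6, no. A one-sided test gives about 63% and 57 per arm about 60% (normal approximations). Adjusting for baseline (variance 8 × (1 − 0.5²) = 6, SD 2.45) gives about 67%. Simulation error does not explain the gap: at 90% power, 100 runs carry ±1.96 × √(0.9 × 0.1 / 100), about 6 points. A four-week interaction limited to these two arms gives 56% if the week-6 means are maintained. It gives about 100% if sham returns to baseline at weeks 12 and 24 while relaxing stays at 2.

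**6. Later cross-check.** The 6-week change SDs in Table 3 (2.04, 1.63, 1.52; n = 41, 45, 51) pool to 1.73, which gives 95%.

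**The case against.** **The stated power may have used the right error term.** The printed power above 90% agrees with the pilot's pooled SD. It can also be reached with 4 and 4 if the contrast counts the return towards baseline that section 9.0 anticipates after treatment. This stands: one might infer that the power was computed with a wrong error term, but the documents do not identify the one used. The interaction power cannot settle it, because it exceeds 95% either way.

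**The week-6 contrast is a choice made here.** Section 9.0 does not say which weeks the post-hoc figure covers. That is true and is part of the fault. The Statistics Section sets the primary aim at week 6, so week 6 is the natural reading.

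**The variance label allows another reading.** Taking 4 as the total variance with ICC 0.5 gives a residual of 2, a change SD of 2.0 (within the pilot's range) and 87% power. That reading contradicts the printed subject component of 4, and 87% is still below 90%.

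**The pilot attribution cannot be disproved.** The protocol does not print the pilot's cross-sectional variance or within-subject correlation, its SDs cover 12 weeks, and it had no sham or untreated arm. The low-intensity arm alone (95% interval for the SD 1.59 to 3.54) does not exclude 2.83. What survives is narrower: the pooled change SDs do exclude it, and the plan does not reconcile them. Under the plan's constant-correlation model, the change SD is the same for any pair of weeks, so the 12-week interval does not remove the conflict.

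**Table 3 is later data.** Agreed: it is reported as an observed result, so it can support the pilot SDs as a cross-check but cannot show what the planning inputs should have been.

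**Conclusion.** The inconsistency holds. Variances of 4 and 4 imply a change SD of 2.83; the pilot named as their source prints 1.5 to 2.2, pooled 1.79. At week 6, the printed inputs give about 51% for relaxing versus sham where the plan claims more than 90%; the pooled pilot SD gives about 94%.

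A reader might infer from the 51% that the trial is too small. The documents do not support that. The printed variance is larger than the pilot's, so it is the conservative input. The interaction power, the comparison with no treatment and the total of 171 stand under either. It would be equally unsafe to treat 94% as settled, since the pilot arms' own SDs span 99% to 78%, and power above 90% needs a change SD no larger than about 1.9.

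These figures assume a random-intercept model, a week-6 change contrast, a two-sided test and 50 evaluable women per arm.

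**What to change.** Wrong as written. In section 9.0:

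- Correct the label of the variance called between-subject, and state the residual and subject variances separately with their derivation from the pilot.
- Name the contrast and the weeks to which the post-hoc power above 90% refers.
- Rerun with more than 100 simulations. Restate week-6 relaxing-versus-sham power at 0.01 as about 94% at the pooled pilot change SD of 1.79, with a range of 99% (SD 1.5) to 78% (SD 2.2), and 51% if 4 and 4 are kept.
- Do not quote a new ICC unless the pilot's subject variance is shown. A residual of 1.6 with a subject variance of 4 would give 4 / 5.6 = 0.71, but no printed data support that 4.
- Cite Table 3 only as a later cross-check (6-week pooled SD 1.73).

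The cost is one rewritten paragraph and one rerun. The downside is that the claim of more than 90% becomes less favourable over part of the range. Sample size and conduct do not change.

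### Section 9.0: the stated inputs give about 52% power for relaxing versus sham at week 6 (two-sided 0.01), not the more than 90% claimed

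*Combined protocol and SAP*

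**What the plan says.** The Power Analysis in section 9.0 opens with "Our power analysis is based on our primary aim to" and restates that aim: the effect of 6 weeks of relaxing acupressure on the BFI against sham or no treatment. The Statistics Section also places the primary question at week 6, and section 9.1 defines evaluability by the baseline and week 6 BFI.

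The simulated model has three groups, "a within-subject factor week (0, 6, 12, and 24), group-by-time interaction and a random subject effect". The means are given as follows: "The mean BFI at baseline is assumed to be 5.5, whereas values at end of treatment were assumed to be 4.5, 3.5, and 2", for no treatment, sham and relaxing in that order. No means are given for weeks 12 or 24.

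The variance sentence reads "The between-subject variance is assumed to be 4 at all time-points" and continues "whereas the variance of the random subject component is taken to be 4 also (yielding an intra-class correlation of 0.5". Of the source it says "These assumed values are estimates based on our pilot data", citing the pilot described in section 1.0.

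With 50 evaluable women per arm, the section claims more than 95% power for the week-by-group interaction at 5%, and that the model can detect a "post-hoc difference between the relaxing acupressure and each of the other two arms with more than 90% power at a reduced 0.01 level". It then turns to the post-treatment period, where "both the no-treatment and the sham acupressure arms will experience a bounce" back towards baseline, and expects larger differences there. The sleep paragraph that follows describes the trial as having more power than it needs for fatigue, and reports that every power figure rests on 100 simulations.

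**The concern.** The 0.01-level claim covers two comparisons with quite different effects: 2.5 points against no treatment and 1.5 points against sham. With the same variance and sample size, the second has far less power.

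Section 4.0 gives sham the task of controlling for placebo effects, so relaxing versus sham is the comparison that isolates the acupoints. If its power is overstated, the reader is misled on the trial's most informative contrast, and the remark about surplus power for fatigue does not cover it. The variance sentence also seems to name the between-subject component twice and never the residual, so the reader cannot tell which input to trust.

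**Working it through.** **Inputs (section 9.0).** Baseline 5.5 in all arms; week 6 means 4.5, 3.5 and 2; 50 per arm; subject variance 4; intra-class correlation 0.5. Sidedness is not stated; two-sided is assumed unless noted.

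**Residual variance.** ICC = subject / (subject + residual), so 0.5 = 4 / (4 + residual) and residual = 4. The subject effect cancels in a change score: variance of change = 2 x 4 = 8, SD 2.83. The standard error of a two-arm difference in change is 2.83 x sqrt(2/50) = 0.566.

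**The plan's other figures.**
- Omnibus interaction, weeks 0 and 6, 5% level: the changes are -1, -2 and -3.5, with sum of squared deviations 3.167. Noncentrality = 50 x 3.167 / 8 = 19.8 on 2 and 147 df, power 98.2% (claimed: more than 95%).
- Relaxing versus no treatment, 0.01: 2.5 / 0.566 = 4.42, power 96.1-96.7% (claimed: more than 90%).

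**Relaxing versus sham, 0.01.** 1.5 / 0.566 = 2.65, against a normal critical value of 2.576.
- Normal approximation 53.0%; t with 98 df 51.2%; mixed-model 441 df 52.6%.
- Simulation (20,000 runs) of this contrast inside the three-arm, four-week model: 52.8% if sham and no treatment return to 5.5, and 52.6% if the week 6 means persist. The later means hardly matter to the week 6 contrast.

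**Other readings of the week 6 comparison.**

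| Reading | Power |
|---|---|
| One-sided 0.01 | 61-63% |
| Two-sided 0.05 | 75% |
| Baseline-adjusted (not described in section 9.0) | 67-69% |
| Total variance 4, ICC 0.5 (SD of change 2.00) | 87-88% |
| Same, one-sided | 91-92% |
| Same, two-sided, baseline-adjusted | 95-96% |

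**Four-week pairwise interaction (3 df), residual variance 4, 0.01.** 56-57% if the week 6 difference is sustained or fully lost; 83% if sham rebounds to 4.0; 90% at about 4.2; 97% at 4.5; more than 99.9% at 5.5.

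**Simulation noise.** With true power 52.6%, the probability of 91 or more successes in 100 runs is about 1e-16. At 90% power the Monte Carlo standard error is 3.0 points with 100 runs and 0.3 points with 10,000.

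**What would give 90% at week 6.** An SD of change of at most about 1.91 (98 df). That is a residual variance of 1.91^2 / 2, about 1.83, and an ICC of 4 / 5.83, about 0.69.

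**The cited pilot (section 1.0).** Pooled SD = sqrt[(13 x 1.5^2 + 14 x 1.6^2 + 13 x 2.2^2) / 40] = 1.79, which gives 94% power. The implied residual variance is 1.79^2 / 2 = 1.60 (95% CI 1.08 to 2.62) and the ICC 4 / 5.60 = 0.71. Over the confidence interval of the SD (1.47 to 2.29), power runs from 99% down to 74%. The arm with SD 2.2 would alone give 78%.

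**Plausibility only.** Table 3 is post hoc. Its pooled SD of 1.73 gives 95%; its two acupressure arms (1.84) give 92%.

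**The case against.** The strongest reply is that the claim belongs to the four-week model, not to a baseline-to-week-6 contrast. The model has four weeks, and the Statistics Section names the group-by-week interaction as the effect of interest. Section 9.0 expects sham to return near its baseline of 5.5 while relaxing holds at 2, and a pairwise interaction test on that profile exceeds 99%. This stands as a possible account of what was simulated. It does not support the claim as written: the section ties the calculation to the 6-week aim, gives numeric means only to the end of treatment, and introduces the rebound afterwards as a second phase with larger differences. If that test was used, the figure relies on the carry-over period, which section 2.0 makes an exploratory aim, and the text should say so.

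The variance sentence could also mean a total variance of 4 across women at each week. That contradicts the stated subject component of 4 and still gives 87-88% two-sided for the change score. It passes 90% only with a further assumption, such as a one-sided test or baseline adjustment. At 87% true power, 91 or more successes in 100 has probability 0.13, so noise could carry that reading, but not the reading with 4 and 4.

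It is also fair that the other two claims are lower bounds, which a smaller variance would meet too. Their agreement shows that 4 and 4 is coherent, not that it was used. Finally, section 9.2 already reports that the sham comparison missed significance, so the practical effect of a correction is limited.

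**Conclusion.** The concern holds. On the stated inputs, relaxing versus sham from baseline to week 6 has about 52% power at two-sided 0.01, roughly 40 points below the claim. The omnibus and no-treatment claims are met, so the surplus-power remark holds for those two comparisons but not for sham.

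This does not show that the trial was truly underpowered against sham. The pilot cited for the inputs points to a smaller residual variance, and its interval excludes 4, so the variances may be what was misreported. What is established is that the stated power and the stated variances cannot both stand for week 6.

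The 52% assumes a two-sided test, a random-intercept model and a residual variance of 4. The pilot comparison uses 12-week change in place of 6-week change, and takes the high-intensity arm's SD as 1.6 from text broken in extraction.

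**What to change.** In section 9.0, state what was simulated: the contrast (baseline to week 6, or the four-week interaction), the sidedness, the means at every simulated week, and the subject and residual variances named separately. Then do one of the following:

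- If a smaller residual variance was used, correct the components and the ICC, and justify them from the cited pilot.
- If 4 and 4 stand, restate relaxing versus sham at week 6 as about 52% at 0.01 (75% at 0.05).

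Limit the surplus-power remark to the omnibus and no-treatment comparisons unless the corrected inputs support it for sham. Rerun with many more than 100 simulations and label the result a correction. Do not use section 9.2 or Table 3 to justify planning assumptions: they are post hoc and appear to be this trial's own data, although the source is not stated.

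The cost is protocol wording and one rerun. The sham figure may become less favourable. No change to sample size or conduct is asked for.

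### The stated power above 90% at the 0.01 level does not follow from the plan's own inputs for relaxing versus sham acupressure: about 51% on the literal variances, about 87% on the more favourable reading

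*Combined protocol and SAP*

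**What the plan says.** The Power Analysis in section 9.0 sets out a mixed model with three arms, four visits (weeks 0, 6, 12, 24), their interaction and a random subject effect. Its inputs are:

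- Means: "The mean BFI at baseline is assumed to be 5.5, whereas values at end of treatment were assumed to be 4.5, 3.5, and 2" for no treatment, sham and relaxing acupressure respectively.
- Variances: "The between-subject variance is assumed to be 4 at all time-points", and "the variance of the random subject component is taken to be 4 also (yielding an intra-class correlation of 0.5").

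It draws two conclusions for fatigue. For the three-arm test, "the power for detecting a significant week-by-group interaction is greater than 95% with a sample size of 50 evaluable participants per treatment arm" "and a 5% level of significance". For relaxing acupressure against each other arm, the same model is said to detect a post-hoc difference "with more than 90% power at a reduced 0.01 level of significance". Only after these two results does the section describe the period after treatment, when it expects the no-treatment and sham arms to drift back towards baseline and the relaxing arm to hold its gain.

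A separate paragraph gives power above 95% for PSQI between any two arms at the 1% level. On method, the section says: "All power calculations are carried out on the basis of 100 simulations in the software PASS 2008". It reports no success counts, point estimates or simulation error.

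**The concern.** The pairwise statement makes one promise about two comparisons of different size. Relaxing versus no treatment has an assumed week-6 difference of 4.5 − 2 = 2.5 points. Relaxing versus sham has 3.5 − 2 = 1.5 points. With the same variance and sample size the second must have much less power, yet both are placed above 90%.

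The sham comparison carries the scientific weight. Section 4.0 says that the sham arm is there to isolate the specific effect of the relaxing points from non-specific effects. If its true design power is nearer one half than nine tenths, a non-significant result says little, and a reader who relies on the stated power would take it as evidence against a specific effect. The section's remark that 50 women per group is more than enough for fatigue would then hold for the three-arm test but not for this contrast.

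The small number of simulations is a further reason to check the figures directly.

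**Working it through.** **Inputs (section 9.0).** n = 50 per arm. Week-6 means 4.5, 3.5 and 2, from a common baseline of 5.5. Intra-class correlation 0.5. Alpha 0.05 for the interaction and 0.01 for pairs. Sidedness is not stated, so I assume two-sided. The contrast is not stated either. I use the change from week 0 to week 6, because the Statistics Section places the primary aim at week 6.

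**Two readings of the variance.**
- Literal: residual 4 and subject 4. ICC = 4/(4 + 4) = 0.5, as stated. Var(change) = 2 × 4 = 8, SD = 2.83.
- Alternative: total variance 4 at each visit with ICC 0.5, so residual 2 and subject 2. Var(change) = 2 × 2 = 4, SD = 2.00. This reading has to set aside the statement that the subject component is itself 4.

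**The plan's interaction figure first.** Use the noncentral F with λ = n × Σ(interaction effect²)/residual variance, on the literal variances.

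| Means after week 6 | Σ effect² | λ | df | Power at 0.05 |
|---|---|---|---|---|
| Weeks 0 and 6 only | 1.583 | 50 × 1.583/4 = 19.8 | 2, 147 | 98.2% |
| Week-6 means maintained | 2.375 | 29.7 | 6, 441 | 99.3% |
| No treatment and sham back at baseline, relaxing stays at 2 | 5.875 | 73.4 | 6, 441 | >99.9% |

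The claim of more than 95% reproduces, and power is higher still with total variance 4.

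**Pairwise power at two-sided 0.01.** Standard error = SD × √(2/50) = 0.2 × SD. Noncentrality = difference/SE. The critical t on 98 df is 2.627.

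| Comparison | Difference | SD of change | SE | Noncentrality | Power |
|---|---|---|---|---|---|
| Relaxing vs no treatment | 2.5 | 2.83 | 0.566 | 4.42 | 96.1% |
| Relaxing vs no treatment | 2.5 | 2.00 | 0.400 | 6.25 | >99.9% |
| Relaxing vs sham | 1.5 | 2.83 | 0.566 | 2.65 | **51.2%** |
| Relaxing vs sham | 1.5 | 2.00 | 0.400 | 3.75 | **86.7%** |

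Pooling the residual over all arms and visits, as the mixed model would, changes little. A 10,000-run simulation of the week-6 contrast gave 52% (literal) and 88% (total variance 4) for relaxing versus sham.

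**What 100 simulations contribute.** The Monte Carlo standard error is √(p(1 − p)/100). At p = 0.95 it is 2.2 points, a 95% margin of 4.3. At p = 0.90 it is 3.0 points, a margin of 5.9. Exact 95% limits are 88.7 to 98.4% for 95 successes in 100, and 82.4 to 95.1% for 90 in 100. With 10,000 runs the margins fall to 0.4 and 0.6 points.

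**Can this noise explain the gap?** If true power were 51.2%, the chance of more than 90 successes in 100 is about 1 × 10⁻¹⁷, so it cannot. If true power were 86.7%, the chance is about 13%, so noise could matter only under the alternative variance reading.

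**PSQI.** No standard deviation of change is given, so the figure cannot be checked. As an illustration, for a 1-point difference with 50 per arm at 0.01, power is 99%, 45% and 17% for an assumed SD of change of 1, 2 and 3.

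**The case against.** The best defence is that the pairwise claim refers to the whole four-visit model. A relaxing-versus-sham group-by-week F test at 0.01 with the expected return to baseline in the sham arm has power above 99.9%, even on the literal variances. But the section states the pairwise power first and brings in the rebound afterwards, as something that would make the differences larger than in the treatment phase. The primary aim is also at week 6. If the week-6 means are instead maintained, the four-visit test gives 56% (literal) or 92% (total variance 4).

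Other choices also pass 90% once total variance is taken as 4: one-sided testing (91%), all 57 randomised per arm counted as evaluable (91%), or adjustment for baseline (95%). The section states none of these for this contrast. On the literal variances the same choices give 61%, 58% and 67%. So the 51% is one reading of ambiguous wording, and that part of the objection stands.

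A reader might infer that 100 simulations discredit every power figure in the plan. The documents do not support that: direct calculation confirms the interaction and the relaxing-versus-no-treatment figures whatever the number of runs.

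A reader might also take section 9.2, where the true-versus-sham difference has p = 0.08, as proof of the planning error. It is not. The observed difference there is 0.66, well below the assumed 1.5, and the pooled SD of 1.7 is below both values used above. At an SD of 1.7 a true difference of 1.5 would have 96% power.

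**Conclusion.** The point holds for one figure. For relaxing versus sham at week 6, the stated power above 90% at the 0.01 level is not delivered by the plan's inputs: about 51% on the literal variances (a shortfall of some 39 points) and about 87% if 4 is the total variance. This rests on a two-sided test of the week 0 to 6 change with 50 women per arm. The literal reading is the only one of the two that fits both stated variances and the stated correlation.

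The rest of the fatigue calculation stands: 98% or more for the interaction and 96% or more for relaxing versus no treatment. It would go too far to conclude that the sample size fails for the three-arm test, or that the number of simulations caused the discrepancy. The cause lies in the inputs or the contrast, and more runs of the same unstated configuration would not cure it. The use of 100 runs without reported error is a minor, separate weakness. The PSQI figure is unverifiable, which is not the same as wrong.

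**What to change.** In section 9.0:

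1. State the residual and subject variances separately, in place of the two overlapping descriptions.
2. Name the pairwise contrast (week 0 to week 6), whether it is adjusted for baseline, and its sidedness.
3. Give the week 12 and week 24 means that entered the simulation, and the standard deviation used for PSQI.
4. Recompute every power figure in closed form or with at least 10,000 simulations. If simulated, give the estimate with its Monte Carlo interval.
5. Report power at 0.01 separately for relaxing versus sham and relaxing versus no treatment. For the sham comparison, replace the claim of more than 90% with the value obtained, about 51% if the literal variances are confirmed.
6. Limit the remark about being more than adequately powered for fatigue to the tests for which it is true.

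The cost is minutes of computing and a few sentences of text. The stated power for the sham comparison becomes less favourable. No change to the design or to the planned analysis follows from this point alone.
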